5.3.2.1 Time since Diagnosis

Time since diagnosis in years at first dose will be calculated as:

$$\text{Time since diagnosis (years)} = (\text{Date of first dose} - \text{Date of diagnosis}) / 365.25$$

Time since diagnosis will also be categorised as:

- $< 2 \text{ years}$
- $\geq 2 \text{ years}$

5.3.2.2 Treatment Compliance

Participants will be expected to dose once daily with 1, 4 or 10 capsules per dose respectively for cohorts 1, 2 and 3.

Compliance will be calculated in 8-week intervals (Weeks 1-8, and Weeks 9-16) as well as across the whole treatment period.

Start and end dates of each treatment period are shown in [Table 1](#).

Expected capsules for each treatment period will be calculated as:

$$\text{Expected capsules} = \text{Number of capsules per dose} * (\text{End date of treatment period} - \text{Start date of treatment period} + 1).$$

Actual capsules taken will be calculated from the dosing log using entries between the start and end days inclusively.

Table 1 Start and End Dates of Treatment Periods for Compliance Calculations

Treatment Period	Start Date	End Date ¹
Weeks 1-8	Day 1	Date of Week 8 visit - 1
Weeks 9-16	Date of Week 8 visit	Date of the last dose of study drug
Whole Treatment Period	Day 1	Date of the last dose of study drug

¹ If a participant prematurely discontinues treatment before the specified end date, the date of last dose will be used for the end date of that treatment period.

Treatment compliance will be calculated as:

$$\text{Treatment compliance (\%)} = 100 * \text{Actual capsules taken} / \text{Expected capsules taken}.$$

Treatment compliance in each period will also be categorised within each treatment period as:

- <80%
- ≥80%

5.3.2.3 Prohibited Concomitant Medications

The following medications are not allowed during the course of the study:

- Systemic immunosuppressive therapy (MTX, apremilast, azathioprine, cyclosporine, 6-thioguanine, mercaptopurine, mycophenolate mofetil, hydroxyurea, and tacrolimus).
- Phototherapy or any systemic medications/treatments that could affect psoriasis or PGA evaluation (including, but not limited to oral or injectable corticosteroids, retinoids, 1,25-dihydroxy vitamin D3 and analogues (protocol versions 4.0 and earlier only, permitted after reconsent to protocol version 5.0), psoralens, sulfasalazine, hydroxyurea, or fumaric acid derivatives).
- Lithium, antimalarials, IM gold, or leflunomide.
- Topical medications/treatments that could affect psoriasis or PGA evaluation (including [but not limited to] high- and mid-potency corticosteroids, anthralin, calcipotriene, topical vitamin D derivatives, retinoids, tazarotene, methoxsalen, trimethylpsoralens, picrolic acid, and tacrolimus) within 2 weeks of the first administration of study drug.
- Live or live-attenuated vaccination.

- Treatment with another investigational drug, biological agent, or device.

Topical unmedicated emollients and low-potency topical steroids are permitted if participants were already using them as part of their care prior to study entry. The participant should not however start new medications or change the dose or frequency of this type during the course of the study.

If a prohibited medication is found to have been used, this will be captured into the protocol deviations log.

5.3.3 Efficacy

5.3.3.1 General

Participants who discontinue treatment but do not withdraw from the study should only have efficacy data collected after discontinuation of treatment included in the supportive estimand for the primary endpoint. For all other analyses, data collected after withdrawal of treatment should be considered as missing.

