4.2 Discontinuation From Study Treatment and/or Withdrawal From the Study

Participants may discontinue from study treatment or withdraw from the study at any time and for any reason without prejudice to their future medical care by the investigator or at the study site. Every effort should be made to keep participants in the study. The reasons for participants discontinuing treatment and/or withdrawing from the study will be recorded in the eCRF.

There are 3 scenarios that result in interruption of the treatment regimen: interruption of study drug, early discontinuation of study drug, and early withdrawal from the study:

- Interruption of treatment is defined as a temporary stopping of study drug that resumes during the treatment period, due to an AE or any other reason. The maximum permitted interruption is 1 week.

- Early discontinuation of treatment is defined as permanent stopping of study drug before completing the visit scheduled for Week 16. Investigators will strive to ensure that a participant who has interrupted treatment for a particular reason will not discontinue treatment unless discontinuation is medically imperative in the investigator's judgment. However, a dose interruption of more than 1 week will result in mandatory discontinuation of treatment.
- Early withdrawal from the study is defined as failing to complete the required follow-up period.

A participant will be discontinued from the study drug or withdrawn from the study for any of the following reasons:

1. The participant experiences treatment failure, demonstrated by the participant commencing an oral agent, biological, or intermediate or high-potency topical therapy.
2. The participant has a serious or intolerable AE that in the investigator's opinion requires discontinuation from study treatment or withdrawal from the study.
3. The participant has symptoms or an intercurrent illness not consistent with the protocol requirements or that justifies withdrawal.
4. The participant is lost to follow-up.
5. Other reasons (eg, pregnancy, development of contraindications to use of study drug).
6. The participant withdraws consent, or the investigator or sponsor decides to discontinue the participant's participation in the study.

A participant may be discontinued from the study drug or withdrawn from the study for any of the following reasons:

1. The participant is noncompliant with the protocol.

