mITT set	Cumulative incidence of rebound at Weeks 20, 24, 28, and 40	To include all data collected after treatment discontinuation	Proportion of participants to rebound in each treatment group at each visit

Summaries and analyses of the secondary endpoints are detailed in full in Section 7.6.2.

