9.3 Part B Analysis

For the Part B endpoints other than those relating to relapse, rebound and duration of effects, a principal strata estimand will be used including all participants in the Part B population with all data included regardless of other intercurrent events.

These endpoints will be summarised at each visit in Parts A and B. Mean (+/- SD) values over time will also be plotted in a figure.

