9.4 Primary Efficacy Analysis

9.4.1 Primary Efficacy Estimand

The primary efficacy estimand will be the effect of EDP1815 compared to placebo on the percentage change from baseline to Week 16 in PASI score. The population summary measure of interest will be the difference in mean percentage change from baseline in PASI score at Week 16.

Intercurrent events will be accounted for in the following manner:

Table 3 Intercurrent Event Strategies for the Primary Estimand

Intercurrent event	Strategy to account for intercurrent event
Protocol deviation with potential to impact efficacy	Treatment policy PASI scores will be used as collected regardless of whether a protocol deviation occurred
Treatment discontinuation for any reason *	While on treatment PASI scores collected more than 4 days after treatment discontinuation will be considered as missing for all timepoints up to Week 16. For the Week 20/follow-up visit, PASI scores will be considered as missing for subjects who did not complete treatment up to Week 16.

* This includes participants who completed the 16-week treatment period but have their Week 16 visit more than 4 days after the end of treatment.

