9.4.2 Supportive Estimands for the Primary Endpoint

For the primary analysis, three supportive estimands will be considered in order to assess the impact of intercurrent events.

Table 4 Supportive Estimands for the Primary Endpoint

Estimand	Purpose	Population	Intercurrent Event Strategy
Primary Supportive Estimand 1	Assess the impact of protocol deviations which may impact efficacy	PP	Protocol deviation with potential to impact efficacy While on treatment (PASI scores collected after the occurrence of the protocol deviation will be considered missing) Treatment discontinuation for any reason before Week 16 While on treatment (as per Primary estimand)

Estimand	Purpose	Population	Intercurrent Event Strategy
Primary Supportive Estimand 2	Assess the impact of treatment discontinuation for any reason	miITT	
Protocol deviation with potential to impact efficacy
 
Treatment policy (as per Primary estimand)
 
Treatment discontinuation for any reason before Week 16
 
Treatment policy (PASI scores collected more than 4 days after treatment discontinuation will be included). Note that Week 20/follow-up data will still only be included for subjects who completed treatment.

Primary Supportive Estimand 3	Assess the impact of treatment discontinuation due to requirement for alternative therapy	miITT	
Protocol deviation with potential to impact efficacy
 
Treatment policy (as per Primary estimand)
 
Treatment discontinuation due to requirement for alternative therapy before Week 16
 
Composite (highest recorded on-treatment PASI score carried forward to all scheduled visits after treatment discontinuation)
 
Treatment discontinuation for any other reason before Week 16
 
While on treatment (as per Primary estimand)

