9.5.6 Partial Relapse, Relapse and Rebound

The following endpoints will be summarised by treatment group and visit in the

- Week 16 responders population:
 - Cumulative incidence of partial relapse at Weeks 20, 24, 28, and 40
 - Cumulative incidence of complete relapse at Weeks 20, 24, 28, and 40
- mITT population:
 - Cumulative incidence of rebound at Weeks 20, 24, 28, and 40

These summary tables will include the number of participants meeting the criteria for the endpoint, and the number of participants 'at risk' of meeting the criteria (the denominator for the cumulative incidence i.e. excluding any participants with a missing status for that endpoint).

For each endpoint, the cumulative incidences for each treatment group will be plotted against time (Week 20 to Week 40) as bars (with an 'error bar' for the corresponding 95% CI).

No inferential analysis of relapse or rebound will be carried out.

Table 6 Intercurrent Event Strategies for Partial Relapse, Relapse and Rebound Endpoints

Endpoint	Intercurrent event	Strategy to account for intercurrent event
Partial Relapse and (Complete) Relapse	Starting a new psoriasis treatment	Composite Starting a new psoriasis treatment is part of the endpoint definition

Endpoint	Intercurrent event	Strategy to account for intercurrent event
Rebound	Starting a new psoriasis treatment	
While in the period following cessation of study treatment, without taking a new psoriasis treatment (analogous to While on treatment)
 
Rebound status will be considered missing from 4 days after the day a new psoriasis treatment is started, onwards, and will not be counted in the denominator during calculation of cumulative incidences

Note that, according to the study design, starting a new psoriasis treatment (synonymous with study treatment failure) should result in a subject completing a PASI questionnaire at an unscheduled Follow-up (Part A)/Early Withdrawal (Part B) visit within 72 hours and then being withdrawn from the study. The above strategies for dealing with the intercurrent event of starting a new psoriasis treatment are included to cover the possibility of a protocol deviation occurring whereby a participant is not withdrawn from the study within 72 hours following the start of a new psoriasis treatment, and to clarify the estimand for rebound.

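### SAP 5.3.3.1 sets post-discontinuation efficacy data to missing without exempting endpoints defined after drug cessation: it contradicts the rebound rules and leaves durations in early stoppers meaningless

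*SAP*

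**What the plan says.** **The general rule.** SAP 5.3.3.1, which opens the efficacy derivations, covers participants who discontinue treatment without withdrawing from the study. They "should only have efficacy data collected after discontinuation of treatment included in the supportive estimand for the primary endpoint". It continues: "For all other analyses, data collected after withdrawal of treatment should be considered as missing". It does not say which of the three supportive estimands it means, gives no grace window and makes no exception by endpoint.

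**Rebound.** SAP 5.3.3.2 defines it within 3 months of stopping study treatment, and SAP section 8 analyses it in the mITT population. For rebound, Protocol Table 7-1 gives the data rule "To include all data collected after treatment discontinuation". SAP 9.5 takes partial relapse, relapse and rebound out of the primary estimand approach. The only missing-data trigger in SAP Table 6 is new therapy: "Rebound status will be considered missing from 4 days after the day a new psoriasis treatment is started".

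**Durations.** SAP 5.3.3.4 starts the clock for duration of therapeutic effect at the end of study treatment. All three durations use mITT (SAP section 8). If the end criterion is never met, the last PASI assessment becomes the end day. Protocol 7.2 and 7.6.3 exclude post-discontinuation data for exploratory endpoints, and the durations are among these.

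**Part B summaries.** SAP 9.3 analyses these "with all data included regardless of other intercurrent events", but the same sentence leaves out relapse, rebound and duration endpoints.

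**The concern.** Rebound and duration of therapeutic effect can be observed only off drug. A rule in the derivations section that blanks off-drug efficacy data, placed just ahead of the definitions of these endpoints, is one a programmer could reasonably apply to them. The data should exist: Protocol 4.2.1 asks that participants who stop drug be encouraged to attend all scheduled visits.

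Two things are at stake. For rebound, part of a stated secondary objective, participants who stop before Week 16 could drop out of numerator and denominator, or stay in, depending on which section the programmer follows. For the durations, the rule does not remove early stoppers. It leaves them in the mean with values that do not measure the endpoint.

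**Working it through.** **1. Who is covered.** Protocol 4.2: "Early discontinuation of treatment is defined as permanent stopping of study drug before completing the visit scheduled for Week 16". The rule therefore reaches participants who stop before Week 16 and remain in follow-up.

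**2. The plan's own figures.** With 50 per active arm, 25 placebo per cohort and 15% discontinuation, completers are 50 × 0.85 = 42.5 (42) and 25 × 0.85 = 21.25 (21), as stated. With difference 20, SD 25 and two-sided 5% (sidedness is not stated; two-sided assumed):
- Pooled placebo: SE = 25 × √(1/42 + 1/63) = 4.98; 20/4.98 = 4.02; power = Φ(4.02 − 1.96) = 98.0%. The plan says more than 95%.
- Within cohort: SE = 25 × √(1/42 + 1/21) = 6.68; 20/6.68 = 2.99; power = Φ(2.99 − 1.96) = 84.9%. The plan says more than 80%.

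Both reproduce, and neither depends on this point.

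**3. Rebound, texts side by side.** SAP 5.3.3.1 blanks the data. Protocol Table 7-1 includes them, SAP 9.5 exempts rebound, and Table 6 blanks only after new therapy. The closing paragraph of SAP 9.5.6 also carries a criterion met before Week 20 to the next analysed visit, which presupposes that such earlier data are used. No precedence rule is given, and SAP Table 8 does not list 5.3.3.1 as a change from the protocol.

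Taking 3 months as 13 weeks, the scheduled PASI visits in the rebound window are:
- stop at Week 4: Weeks 8, 12, 16
- stop at Week 8: Weeks 12, 16, 20
- stop at Week 12: Weeks 16, 20, 24

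Read literally, 5.3.3.1 blanks every one of these.

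**4. Durations.** Duration = End Day − Start Day. Take a participant whose Week 8 PASI is on Day 57, who stops drug on Day 80 and stays in the study, with no new psoriasis treatment (illustrative days, consistent with the visit schedule).
- *Therapeutic effect:* Start Day = 80. If the loss criterion is first met at Week 16 (Day 113), the duration is 113 − 80 = 33 days. Under 5.3.3.1 the last retained PASI is Day 57, so the fallback gives 57 − 80 = −23 days. In general the last retained PASI is on or before the stop day, so the result is zero or negative. SAP 5.3.3.4 gives zero its own meaning: effect already lost by end of treatment.
- *Treatment success:* if PASI-50 is first reached on Day 57 and still held at Week 20 (Day 141), the duration is at least 141 − 57 = 84 days. Under the rule it is 57 − 57 = 0.

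No text rescues these endpoints. The SAP 9.5 exemption does not name them, 9.3 leaves them out, and Protocol 7.2 and 7.6.3 point the same way as 5.3.3.1.

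**5. Size.** Early discontinuers at the 15% ceiling: 225 × 0.15 = 33.75, about 34 (7.5 per active arm, 11.25 in pooled placebo). If all were dropped, rebound denominators would fall from 50 to 42.5 and from 75 to 63.75. At 5% or 10% discontinuation the totals are 11.25 and 22.5.

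**6. Possible shift in rebound incidence.** The documents give no rebound rates. Assuming 5% in completers and 5% to 40% in early stoppers, overall incidence is 0.85 × 5% + 0.15 × 5% = 5.0%, rising to 0.85 × 5% + 0.15 × 40% = 10.25%. It is 5% if early stoppers are dropped.

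**7. Further mismatch.** Under the primary estimand, "PASI scores collected more than 4 days after treatment discontinuation will be considered as missing for all timepoints up to Week 16". Section 5.3.3.1 has no such window. Only Primary Supportive Estimand 2 uses off-drug scores ("PASI scores collected more than 4 days after treatment discontinuation will be included").

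**The case against.** The strongest reply is that specific text governs general text. For rebound, four endpoint-specific provisions keep the data against one generic sentence, so a careful analyst would keep them. That stands. A reader might infer that the SAP deletes the rebound data, but the documents support only a contradiction.

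Other limits also stand:
- A reader might take SAP 9.3 as telling the analyst to include all data for rebound and durations. Its opening words leave those endpoints out; it conflicts with 5.3.3.1 only for the other Part B summaries.
- A reader might think that completers' Week 20 to 40 data, or relapse, are lost. Completers are not early discontinuers. Relapse uses Week 16 responders, whom Protocol 6.1.1 defines as on treatment at that visit.
- The 34 is a loose ceiling. The 15% is itself a maximum, those who also leave the study have no later data to blank, and those starting new psoriasis treatment should be withdrawn (SAP 9.5.6).
- Nothing in the documents shows that early stoppers rebound more often.
- SAP 9.5.6 plans no inference on relapse or rebound, and the durations are exploratory summaries.

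These points limit the consequence. They do not answer the duration problem, where no specific text exists to prevail.

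**Conclusion.** The point holds in two parts of different strength. For rebound, SAP 5.3.3.1 contradicts Protocol Table 7-1 and SAP 9.5 and 9.5.6; applied literally it would blank the rebound visits of participants who stop before Week 16 and stay in the study. For duration of therapeutic effect, the rule stands unopposed and, with the fallback end date, yields values of zero or below unless a new-treatment date supplies the end. Remission and treatment-success durations are truncated.

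The number exposed is at most about 34 of 225, and the true number cannot be derived because retention after discontinuation is not given. This rests on the protocol's definition of early discontinuation and on a literal reading of 5.3.3.1. The change should be made before the Part B outputs are programmed.

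**What to change.** In SAP 5.3.3.1:
- limit the rule to endpoints analysed under the primary estimand approach, with the 4-day window of SAP Table 3;
- name Primary Supportive Estimand 2 as the analysis that includes off-drug data;
- state that the rule does not apply to relapse and rebound (governed by Table 6 and 9.5.6), to the Part B summaries (governed by 9.3), or to the duration endpoints.

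For the durations, state that PASI after cessation is used up to the start of a new psoriasis treatment, as the definitions in SAP 5.3.3.4 already imply, and add an intercurrent-event row for them. Align the exploratory-endpoint sentences in Protocol 7.2 and 7.6.3, or list the departure in SAP Table 8.

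The cost is a few sentences and one table row. No new data, visits or sample size are needed, and the primary analysis does not change.

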5.3.3.2 Psoriasis Area and Severity Index

PASI score will be calculated within the eCOA system and taken directly from the supplied data. Further information on the scoring of the PASI is provided in [Section 16](#).

PASI-50, PASI-75, PASI-90 and PASI-100 responses are defined respectively by at least a 50%, 75%, 90% and 100% reduction from Baseline in the PASI score.

Response at Week 16 is defined as achieving PASI-50 or greater at the Week 16 visit.

Partial relapse is defined, after the Week 16 visit, as loss of PASI-50 response after cessation of study treatment, or the participant begins a new treatment for psoriasis.

Relapse is defined, after the week 16 visit, as an increase in PASI score to the baseline value or greater, or the participant begins a new treatment for psoriasis.

Rebound is defined as an increase in PASI score to 125% of baseline value or above, or onset of new pustular/erythrodermic psoriasis, within 3 months of cessation of study treatment.

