- k Skin plaque biopsies (ie, a 4 mm punch biopsy, performed pre-dose by suitably trained study personnel and processed as per laboratory manual) are to be performed after all other assessments have been completed at the end of Visits 2 and 10.
- l Digital photographs should be taken of up to 6 lesion sites that have a lesion area ideally greater than 2 cm by 2 cm at baseline. The same locations photographed at baseline should be followed throughout the study for each participant.
- m Stool samples are to be collected within the 48 hours preceding each visit of stool sample collection.
- n Investigator rating scales. Participants will be asked to withhold all emollients or moisturizers on the day of these study visits until all study assessments are completed.
- o Inclusion criterion #4 (mild to moderate plaque psoriasis with plaque covering BSA of $\ge 3\%$ and $\le 10\%$, PASI score of ≥ 6 and ≤ 15 , and PGA score of 2 or 3) should be reconfirmed at the baseline visit prior to randomization.
- p Participant-reported assessments.
- q Study staff will review the dosing diaries with participants at each visit when diaries are collected. Diaries will be reviewed for completeness and accuracy, and participants will be coached as needed on compliance with the protocol.

Table 6-2 Schedule of Post-Treatment Follow-Up Assessments – Part B

Procedure	Post-Treatment Follow-Up – Part B ^a			Early Withdrawal Visit ^a
Visit number	12^b	13^b	14^c	
Months (after the End of Treatment)	2	3	6	
Weeks	24	28	40	
Day	169	197	218	–
Visit window (days)	162-176	190-204	204-232	–
BSA involvement (%), PGA, PASI ^d	X	X	X	X
LSS, mNAPSI ^d	X	X	X	X
PSI, DLQI ^e	X	X	X	X
Concomitant medication review	X	X	X	X

^a Participants who withdraw from the study during Part B should complete the final assessments at the Early Withdrawal Visit (where relevant and when possible, this should be arranged within 72 hours of the start of a new psoriasis treatment).

^b All participants will attend Visits 12 and 13, unless they are considered a ‘treatment failure’ or meet the criteria for rebound.

^c Only participants who are classified as responders at Week 16 (Visit 10) and have not relapsed at Week 28 (Visit 13) will be eligible for Visit 14 (Week 40).

^d Investigator rating scales. Participants will be asked to withhold all emollients or moisturizers on the day of these study visits until all study assessments are completed.

^e Participant-reported assessments.

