6.1 Efficacy Assessments

6.1.1 Psoriasis Area and Severity Index Score

The PASI score will be assessed as described by Langley and Ellis (2004). The PASI is a physician assessment that combines the assessment of the severity of and area affected by psoriasis into a single score in the range 0 (no disease) to 72 (maximal disease). The absolute PASI score in this study is used as part of inclusion criterion #4. The PASI percentage response rates are efficacy endpoints (ie, PASI-50, PASI-75, PASI-90, and PASI-100). For example, the percentage of participants who achieve a 75% or greater reduction in PASI score from baseline is represented by the PASI-75 value. Details of the PASI assessment will be provided in the relevant training material.

Response Definitions based on PASI score at Week 16:

- **Responders:** Participants on treatment achieving PASI-50 or greater at Week 16 visit
- **Relapse:** Increase in PASI score to baseline value or greater, or participant begins a new treatment for psoriasis
- **Partial Relapse:** Loss of PASI-50 response after cessation of study treatment
- **Rebound:** Increase in PASI score to 125% of baseline value or above, or onset of new pustular/erythrodermic psoriasis within 3 months of cessation of study treatment
- **Duration of remission:** Time from first achievement of PASI-100 to loss of PASI-100
- **Duration of treatment success:** Time from first achievement of PASI-50 to loss of PASI-50
- **Duration of therapeutic effect:** Time from cessation of study treatment until increase of PASI to 50% of maximum improvement from baseline

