- Placebo 10 capsules
- EDP1815 10 capsules
- All Placebo
- All EDP1815
- Total

For concomitant medication, efficacy and safety outputs, columns will be ordered and labelled as follows:

- All Placebo
- EDP1815 1 capsule
- EDP1815 4 capsules
- EDP1815 10 capsules
- All EDP1815 (concomitant medication and safety only)

For the efficacy analyses, if the 3 cohorts of placebo participants are found to be too heterogeneous for pooling, selected efficacy tables will also be presented by treatment within cohort, in which case columns will be ordered and labelled as:

- Placebo 1 capsule
- EDP1815 1 capsule
- Placebo 4 capsules
- EDP1815 4 capsules
- Placebo 10 capsules
- EDP1815 10 capsules

For the primary analysis:

- For study disposition summaries where it is appropriate to report information on participants who failed screening, the enrolled population will be used.
- For safety summaries, the safety population will be used.
- For all other summaries and analyses the mITT population will be used, with selected efficacy outputs reproduced using the per-protocol population.

For the final analysis:

- For partial relapse and complete relapse endpoints analysis Week 16 Responders population will be used.
- For duration endpoints and rebound analysis mITT population will be used.
- For or all other summaries and analyses the Part B population will be used.

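### The rebound derivation does not separate PASI already at or above 125% of baseline when dosing stopped from PASI that first reached that level afterwards.

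*SAP*

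**What the plan says.** SAP 5.3.3.2: "Rebound is defined as an increase in PASI score to 125% of baseline value or above". New pustular or erythrodermic disease also counts, and the window is 3 months from stopping study treatment. Protocol 6.1.1 has the same threshold: "Increase in PASI score to 125% of baseline value or above". Both compare with the pre-treatment baseline, not with the value at the end of dosing.

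On population, SAP Section 8 states: "For duration endpoints and rebound analysis mITT population will be used". SAP 9.5.6 lists "Cumulative incidence of rebound at Weeks 20, 24, 28, and 40" under mITT. Its denominator leaves out only participants whose status is missing, and no inferential analysis is planned.

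The neighbouring endpoints do account for disease state at the end of treatment. For relapse, SAP 5.3.3.2 says "Relapse is defined, after the week 16 visit, as an increase in PASI score to the baseline value or greater", and both relapse endpoints use Week 16 responders only. Duration of therapeutic effect (SAP 5.3.3.4) has explicit rules for participants who never improved and for those who had already lost the effect when treatment ended.

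Protocol Table 6-2, footnote b, sends everyone to Visits 12 and 13 unless they are a treatment failure "or meet the criteria for rebound".

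**The concern.** Take a participant with PASI 8 at baseline, 10.5 at Week 16 and 10.5 at Week 20. The threshold is 1.25 × 8 = 10. Nothing changed on stopping, yet the Week 20 value is at or above 125% of baseline, falls within 3 months of cessation, and no derivation rule keeps it out of the rebound count.

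The Week 16 value might itself be counted. The last paragraph of SAP 9.5.6 assigns a criterion met before Week 20 to the next scheduled visit and all later ones. SAP 5.3.4.2 ends the treatment phase at Day 112, and Protocol Table 6-1 puts the Week 16 visit at Day 113. A PASI that reflects 16 weeks of dosing could thus be taken as an event after cessation and carried to Week 40.

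Placebo is the only yardstick for rebound, and readers will compare raw percentages. If active treatment works, fewer active than placebo participants will have worsened on treatment. The carried-over cases then raise the placebo figure more and can hide a withdrawal effect on active. Footnote b may also release these participants from the Week 24 and 28 visits under a label that does not fit them.

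**Working it through.** **Inputs from the documents.** SD of percent change 25 and a 20-point difference from placebo; 75 pooled placebo and 50 per active dose randomised (150 active); 63 placebo (3 × 21) and 42 per dose expected at Week 16 (SAP Section 6). Baseline PASI is 6 to 15 (Protocol 4.1.1), so the threshold is a rise of 1.5 to 3.75 points.

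**Assumptions, not in the documents.** Normal percent change; placebo mean 0, -10 or -20%, unchanged after Week 16; active 20 points lower; equal correlation between visits of 0.7 to 0.85; no missing data.

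**The plan's own figure.** It states no rebound rate, so only the power statement can be checked (two-sided 5%).
- Pooled, 63 v 42: 20 / (25 × √(1/63 + 1/42)) = 4.02; 4.02 − 1.96 = 2.06; power 98.0% (stated: more than 95%).
- Within cohort, 21 v 42: 20 / (25 × √(1/21 + 1/42)) = 2.99; 2.99 − 1.96 = 1.03; power 84.9% (stated: more than 80%).

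Both reproduce.

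**Step 1: already at or above 125% at Week 16.** P = 1 − Φ((25 − mean)/25).

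| Placebo / active mean | Placebo | Active | Expected of 75 / 150 |
|---|---|---|---|
| 0 / -20% | 15.9% | 3.6% | 11.9 / 5.4 |
| -10 / -30% | 8.1% | 1.4% | 6.1 / 2.1 |
| -20 / -40% | 3.6% | 0.5% | 2.7 / 0.7 |

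The placebo share of these participants is 69% to 79%. With a 10-point effect it is 50% to 56%. With no effect it is 33% (75 of 225).

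**Step 2: how many are counted later.** Take Weeks 16, 20, 24 and 28 as equally correlated, with a = (25 − mean)/25 and q(u) = Φ((a − √ρ·u)/√(1 − ρ)), u standard normal. Carried over = E[(1 − q)(1 − q³)]; newly met = E[q(1 − q³)]. At means -10 and -30%, as percentages of all participants in the arm:

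| | ρ = 0.7 | ρ = 0.85 |
|---|---|---|
| Placebo, carried over | 5.7% | 6.6% |
| Placebo, newly met | 10.1% | 6.8% |
| Placebo, carried-over share | 36% | 49% |
| Active, carried over | 0.7% | 1.0% |
| Active, newly met | 2.4% | 1.7% |

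So 70% to 81% of placebo participants past the threshold at Week 16 are past it again by Week 28.

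**Step 3: sensitivity.** At Week 20 alone, with placebo mean 0 to -20% and Week 16 to 20 correlation 0.5 to 0.9, 21% to 73% of placebo cases were already past the threshold at Week 16.

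**Step 4: masking.** Add a supposed true withdrawal rebound of 5% on active and none on placebo. Counting only carried-over cases besides, active shows 5.7% to 6.0% and placebo 5.7% to 6.6%: roughly a tie.

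**The case against.** The best reply is that the definition already deals with timing. It places the increase within 3 months of cessation, Protocol Table 7-1 takes data from after discontinuation, and SAP Table 6 refers to the period after cessation. This stands in part: PASI values from during dosing are not counted as such, and a reader who infers that rebound has no link to the post-treatment period goes too far. On a natural reading, the 10.5-to-10.5 participant has had no increase in the window. But no derivation rule puts that reading into effect, and programmers could differ.

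A reader might also infer that the table would reverse the sign, about 6% active against 8% placebo in the 5% scenario. That needs every participant past the threshold at Week 16 to stay past it (1.4 + 5 = 6.4% v 8.1%). With 70% to 81% persisting, the carried-over cases give a tie. Nor do the documents show that the misclassified cases are mostly placebo; that depends on efficacy.

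Three further points stand. Status becomes missing from 4 days after a new psoriasis treatment, and SAP 7.7 leaves early withdrawers' follow-up data out of by-visit tables, so some of the worst cases drop out. Week 16 worsening is visible in the waterfall plot, visit summaries and listings, though not linked to the rebound count. And removing participants already past the threshold from the denominator would be a poor repair: it conditions on an outcome that treatment affects and makes a flare from 126% to 200% of baseline uncountable.

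**Conclusion.** The point holds as a gap in the derivation. Rebound is referenced to pre-treatment baseline, counted in all mITT participants, and silent on those already at or above 125% when dosing ended. Worsening that began on treatment and persists can be reported as rebound after cessation.

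Its size cannot be fixed from the documents. On the stated assumptions it is 3.6% to 15.9% of placebo and 0.5% to 3.6% of active already past the threshold at Week 16, and about 36% to 49% of placebo PASI rebounds through Week 28 at a placebo mean of -10%. The direction, more placebo than active, rests on the drug working. Masking of a withdrawal effect is possible; a reversed comparison is not shown. The analysis is descriptive, but it is the planned answer to a secondary objective with safety relevance, so the change should be made.

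**What to change.** In SAP 5.3.3.2, SAP 9.5.6 and the rebound table, keep the planned mITT denominator and split the PASI limb of rebound into two rows:
- (a) newly met: below 125% of baseline at the last on-treatment assessment and at or above 125% afterwards;
- (b) already at or above 125% at the last on-treatment assessment.

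Use (a) to address the objective, and show (b) and the total beside it. State that the Week 16 assessment is the end-of-treatment reference and not itself a rebound visit.

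The sponsor should reconcile Protocol Table 6-2, footnote b, with whichever definition is adopted. SAP 5.3.3.1, which treats post-discontinuation efficacy data as missing outside the primary endpoint's supportive estimand, also needs reconciling with Protocol Table 7-1, which includes such data for rebound.

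The cost is one more derivation and two table rows, from data already collected. The split does not remove ordinary fluctuation across the threshold after Week 16. In the -10/-30% scenario row (a) would still hold 6.8% to 10.1% of placebo and 1.7% to 2.4% of active with no true rebound in either arm, and the report should acknowledge this.
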